3.2.8 Antibiotic allergy and adverse event

3.2.8.1. Anaphylaxis: To be considered anaphylaxis, the patient must have had ≥1 of the following 3 criteria that a medical team member attributed to an antimicrobial:

- Acute onset of skin or mucosal tissue changes (hives, itching/flush, lip/tongue/uvula

swelling) over minutes/hours, accompanied by

- respiratory compromise (dyspnea, wheeze, stridor, hypoxemia), AND/OR
 - reduced blood pressure or symptoms/signs of end organ dysfunction from shock
- Rapid onset of two or more of the following
- involvement of the skin-mucosa (hives, itch, flush, swollen lips/tongue/uvula)
 - respiratory compromise
 - reduced blood pressure or associated symptoms/signs
 - persistent gastrointestinal symptoms/signs (crampy abdominal pain, vomiting)
- Reduced blood pressure after exposure to a known allergen for that patient

3.2.8.2 Antimicrobial-associated renal injury: To be considered Antimicrobial-associated renal injury, a medical team member must have attributed the renal injury to the Antimicrobial, and the severity of the renal injury must meet one of these (RIFLE criteria):³

- Risk:* GFR decrease >25%, serum creatinine increased 1.5 times or urine production of <0.5 ml/kg/hr for 6 hours
- Injury:* GFR decrease >50%, doubling of creatinine or urine production <0.5 ml/kg/hr for 12 hours
- Failure:* GFR decrease >75%, tripling of creatinine or creatinine >355 µmol/l (with a rise of >44) (>4 mg/dl) OR urine output below 0.3 ml/kg/hr for 24 hours
- Loss:* persistent AKI or complete loss of [kidney function](#) for more than 4 weeks
- End-stage renal disease:* need for renal replacement therapy (RRT)

3.2.8.3 Antimicrobial-associated hepatitis: To be considered antimicrobial-associated hepatitis, a medical team member must have attributed the hepatitis to the antimicrobial, and the severity of the hepatitis must meet this FDA criteria for hepatic adverse events:

- ALT > 3x the upper limit of normal

3.2.9 *Clostridioides difficile* infection: defined as a positive PCR, culture or ELISA test for *Clostridioides difficile* toxin in the context of diarrhea within hospital (or 90 days, whichever occurs first) of bacteremia diagnosis.

3.2.10 Risk of colonization/infection with antimicrobial resistant organisms in hospital– defined as a positive culture yielding a highly resistant microbial organism (HRMO) as defined by a modification of the Dutch nosocomial infection surveillance guidelines from the date of index blood culture until 28 days or hospital discharge whichever is first. This broad definition includes methicillin-resistant *Staphylococcus aureus*, vancomycin-resistant Enterococci spp, extended spectrum beta-lactamase producing Enterobacteriaceae, carbapenem-resistant Enterobacteriaceae, carbapenem-resistant *Acinetobacter* spp; or Enterobacteriaceae resistant to at least two of fluoroquinolones, aminoglycosides or trimethoprim-sulfamethoxazole, *Acinetobacter* spp resistant to at least two of fluoroquinolones, aminoglycosides or ceftazidime; or non-Enterobacteriaceae resistant to at least three of fluoroquinolones, aminoglycosides, carbapenems, ceftazidime or piperacillin.⁴ We will also conduct a sensitivity analysis limited to isolation of these organism(s) only from sterile site specimens (such as blood, cerebrospinal fluid, peritoneal fluid, synovial fluid, pleural fluid, and tissue biopsies).

3.2.11 Antibiotic-free days (of 28) - defined as the number of days during the 28 days after the start of adequate antibiotics in which patients did not receive any dose of any antibiotic. Antifungal and antiviral therapies will not be considered in this analysis. This definition will include all antibiotics, irrespective of their activity against the pathogen(s) in the initial blood culture.

4. Sample size calculation

The primary analysis will assess whether 7 days of treatment is associated with a non-inferior 90-day mortality rate in comparison to 14 days of treatment. We require 1,686 patients per arm to establish a non-inferiority margin of +4% absolute increase in mortality (baseline mortality 22%)⁵ power 80%, alpha 0.025, one-sided equivalence test). We have inflated this to account for a maximum of 5% loss-to-follow-up, and have incorporated early stopping rules to account for the 3 interim analyses (coefficient 1.024)^{6,7} for a total sample size of 3626. Recent landmark trials in with similar baseline mortality rates have used +4% as a non-inferiority margin;^{8,9} the U.S. FDA has recommended a similar margin for analogous industry-sponsored trials.¹⁰ The PneumA study of 8 vs 15 day treatment for VAP used a non-inferiority margin of 10%,¹¹ as have other recent prominent infectious diseases non-inferiority trials,^{12,13} but we believe lower non-inferiority margins are desirable, when feasible, for the outcome of mortality.

5. Statistical analysis

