2.2 Secondary outcome measures

Secondary outcomes that we hypothesize to be non-inferior with 7d vs 14d treatment include:

- hospital mortality
- ICU mortality
- relapse rates of bacteremia with the same organism within 30 days
- ICU length of stay and ICU-free days (of 28)
- hospital length of stay and hospital free-days (of 28)
- mechanical ventilation duration and mechanical ventilation-free days (of 28)
- vasopressor duration and vasopressor-free days (of 28)

Secondary outcomes that we hypothesize to be superior with 7d vs 14d treatment include:

- antibiotic allergy and adverse events in hospital
- rates of *C. difficile* infection in hospital
- rates of secondary nosocomial infection/colonization with antimicrobial resistant organisms in hospital
- antibiotic-free days (of 28)

3. Outcome definitions

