5.2 Analysis of secondary outcomes

Mortality rates at other time points will be calculated in a similar manner to 90-day mortality. We hypothesize that mortality rates will be non-inferior with 7 days of treatment using the same 4% non-inferiority margin, and relapse of bacteremia using a 2% absolute margin. Continuous secondary outcomes, including ICU, hospital, ventilation and vasopressor free-days by day 28 will be summarized as means and difference in means with 95% CIs as well as medians and difference in medians using quantile regression. For ICU, hospital, ventilation and vasopressor free-days by 28, a 2-day margin will be used for assessing non-inferiority.

We hypothesize that 7 days of treatment will be superior to 14 days of treatment for: antibiotic allergy and adverse events, rates of *C. difficile* infection in hospital, rates of secondary nosocomial infection/colonization with antimicrobial resistant organisms in hospital, and antibiotic-free days (of 28). The evaluation of allergy and adverse events will be important but these analyses are likely to be underpowered due to low event rates, despite the large trial sample size. Antibiotic allergy and adverse events, *C. difficile* infection and secondary nosocomial infection/colonization with antimicrobial resistant organisms are binary outcomes, and we will examine via chi-square tests of proportions. Antibiotic-free days (of 28) will be summarized as means and difference in means with 95% CIs as well as medians and difference in medians using quantile regression.

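### Renal injury and hepatitis count only if a team member blames an antimicrobial; after day 7 that judgement may differ by arm and shift the superiority test towards 7 days, by an unknown amount

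*SAP*

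**What the plan says.** Section 3.2.8 of the SAP defines three antibiotic harms. Renal injury (3.2.8.2) has two conditions: "a medical team member must have attributed the renal injury to the Antimicrobial", and one of the RIFLE classes must be reached. Hepatitis (3.2.8.3) also has two: "a medical team member must have attributed the hepatitis to the antimicrobial", and ALT above three times the upper limit of normal. Anaphylaxis (3.2.8.1) needs clinical criteria "that a medical team member attributed to an antimicrobial".

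Section 2.2 lists the outcome as "antibiotic allergy and adverse events in hospital", among those expected to be better with the shorter course. Section 5.2 repeats this: "We hypothesize that 7 days of treatment will be superior to 14 days of treatment for: antibiotic allergy and adverse events". On the test, it says that these outcomes "are binary outcomes, and we will examine via chi-square tests of proportions". It also warns that "these analyses are likely to be underpowered due to low event rates, despite the large trial sample size".

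Section 5.1, in explaining the modified intention-to-treat analysis, treats day 7 as the point at which the two assignments separate.

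The SAP gives no rule or time window for attribution, no masked adjudication, and no analysis of threshold-meeting events irrespective of attribution. It does not say whether treatment is masked.

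**The concern.** Attribution to a drug needs a candidate drug. Up to day 7 the arms have the same assigned exposure. From day 8 to day 14 only the 14-day arm is on assigned treatment, and the in-hospital window includes those days. The same creatinine or ALT rise on day 11, from sepsis or another cause, has an obvious suspect in one arm and a weaker one in the other. Whether it counts can then depend on the allocated duration as well as on the injury.

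Less drug toxicity and less opportunity to blame the drug would look the same in the chi-square test, and nothing in 5.2 separates them. Elsewhere the SAP is less exposed: *C. difficile* infection (3.2.9) rests on a laboratory test plus diarrhea with no attribution step, and resistant organisms (3.2.10) have a planned sensitivity analysis on a stricter definition.

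At stake is a secondary claim that shorter treatment causes less renal or hepatic harm. The primary mortality conclusion is not affected.

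**Working it through.** **The plan's own figure.** The SAP gives no figure for the adverse-event test, so only the sample size can be reproduced. Section 4 has 22% mortality, a 4-point margin, one-sided alpha 0.025 and power 80%: (1.960 + 0.842)² × 2 × 0.22 × 0.78 / 0.04² = 1,684 per arm, against 1,686 stated. Then 2 × 1,686 × 1.05 × 1.024 = 3,625.6, which gives the stated 3,626. With 1:1 allocation (assumed) that is 1,813 per arm.

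**Common set-up (assumed).** One binary outcome, two-sided 5% test (5.2 states neither alpha nor sidedness), and all 1,813 patients per arm at risk after day 7. The last point overstates the effect, since patients discharged or dead by then cannot contribute. True injury is equal in both arms, so the chance of a significant result favouring 7 days should be 2.5%.

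z = (p14 − p7) / √[2p̄(1 − p̄)/1,813]; chance ≈ 1 − Φ(1.96 − z).

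**Model A (all rates assumed).** True drug-related events are 1% in each arm. Background injury on days 8-14 occurs in a share b of patients, and a share a of it is attributed while on drug. Off-drug attribution is a fraction r of the on-drug rate.

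p14 = 0.01 + b·a; p7 = 0.01 + b·a·r.

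Example with b = 3%, a = 10%, r = 0: p14 = 0.013, p7 = 0.010, p̄ = 0.0115, SE = 0.00354, z = 0.847, chance = 1 − Φ(1.113) = 13%.

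| a | r | b = 3% | b = 6% | b = 10% |
|---|---|---|---|---|
| 10% | 0 | 13% | 36% | 70% |
| 10% | 0.5 | 6% | 11% | 21% |
| 5% | 0 | 6% | 13% | 27% |
| 5% | 0.5 | 4% | 6% | 9% |

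With b = 1% and r = 0 the chance is 4.8% (a = 10%) or 3.5% (a = 5%).

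**Model B (all rates assumed).** Events meeting a threshold occur at equal rates in both arms, early (to day 7) and late. Of these, 30% are attributed on drug and a smaller share q after stopping.

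p14 = 0.30 × (early + late); p7 = 0.30 × early + q × late.

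Example with early 2%, late 1%, q = 20%: p14 = 0.009, p7 = 0.008, z = 0.33, chance = 5.1%.

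| Early, late | q = 20% | q = 15% | q = 10% | q = 5% |
|---|---|---|---|---|
| 2%, 1% | 5.1% | 7.2% | 10.0% | 13.5% |
| 5%, 5% | 14.9% | 29.2% | 48.7% | 69.6% |
| 10%, 10% | 26.1% | 52.6% | 78.9% | 94.3% |

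With q = 30%, or with the thresholds applied irrespective of attribution, the chance is 2.5%.

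**How few events matter.** With 18 events in the 7-day arm (about 1% of 1,813), 32 in the 14-day arm gives z = 1.99. Fourteen extra attributions are enough for nominal significance.

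**The case against.** Attribution plus an objective threshold is a reasonable way to define antimicrobial-associated injury, and it contradicts nothing in the SAP. The mechanism needs attributors who know whether the drug is being given. The SAP accompanies a separate protocol, where masking and attribution procedures would usually be found, and placebo masking would hide exactly that knowledge. Every rate in the models is assumed. Off-drug attribution is unlikely to be zero: injury can be noticed after a drug stops, and 3.2.8 does not limit the antimicrobial to the assigned course, so another antibiotic given to a 7-day patient can also be blamed. The SAP already concedes low power for this secondary outcome. Counting every RIFLE-level injury from any cause would measure illness as much as antibiotic harm. It may not be possible with the data collected, and it would not remove bias if patients still on drug are tested more often.

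Most of this stands, and it limits the point. It bears on the size of the effect and on whether the condition is met, not on the direction if it is met. The power caveat is no protection against bias, because at low counts a few differential attributions suffice. The dilution argument is a reason to add the any-cause comparison beside the attributed one, not to substitute it.

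A reader might infer that attribution is far more likely in the 14-day arm, or that a false superiority finding is probable. The SAP has no figure to support either.

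**Conclusion.** The point holds as a conditional one. As defined, renal injury and hepatitis can be counted differently by arm after day 7 if attributors know who is still on the drug, and the shift would favour 7 days. The SAP neither states nor rules out that condition, and it provides no analysis that would reveal the shift.

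The size is unknown. Under the assumed inputs, the chance of falsely favouring 7 days goes from 2.5% to roughly 4-14% when late events are few (about 1%) or when some attribution continues off drug. The second route has an upper limit: with late injury at 10%, the chance reaches 21-26% even when off-drug attribution is half or two thirds of the on-drug rate. Values of 70% or more need common late injury together with a wide attribution gap. The low event rates that the SAP expects point to the lower end.

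Anaphylaxis carries the same attribution condition, but its onset within minutes or hours makes misattribution of late background events less plausible. It need not be treated in the same way.

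**What to change.** In 5.2, with a cross-reference from 3.2.8.2 and 3.2.8.3:

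- Where creatinine, urine output and ALT were recorded irrespective of attribution, add a between-arm comparison of all events meeting the stated RIFLE or ALT threshold, whoever or whatever was blamed. Keep the attributed analysis. Claim superiority for these two components only if the two analyses agree in direction.
- Where the measurements were not recorded in this way, report attributed renal injury and hepatitis descriptively by arm, make no superiority claim for them, and state that attribution depends on exposure.

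The cost is a few sentences and one further tabulation, or a weaker claim if the data do not exist. Any-cause events add background noise and reduce precision for truly drug-related injury. Agreement in direction is a safeguard rather than proof, since unequal laboratory testing after day 7 could still affect both analyses.

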5.1 Analysis of primary outcome

The BALANCE Trial will be conducted, analyzed and reported according to CONSORT guidelines, including analyzing patients in the groups to which they were assigned (adherent to the intention-to-treat principle).¹⁴ We will also include a per-protocol analysis. Inferences that 7 day treatment is non-inferior to 14 day treatment will be stronger if this finding is confirmed in both intention-to-treat and per protocol analyses.¹⁵ We will also perform a modified intention-to-treat analysis (mITT), excluding patients that die before day 7 of treatment, given that these patients die prior to divergence in treatment assignment.¹⁶ The primary analysis will examine whether 90-day mortality is non-inferior in the 7 vs. 14 day treatment group, as determined by whether the 95.7% confidence interval excludes a 4% absolute increase in mortality. Results will also be reported as relative risks with confidence intervals.

In a secondary adjusted analysis we will use generalized linear mixed models with random effects for center (which was a stratification variable) - with log-link and binomial distribution and report relative risks and confidence intervals. If this model fails to converge we will use modified Poisson regression.¹⁷

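### Section 3.2.10 lets a resistant index blood isolate count as a secondary resistant-organism event, which dilutes a superiority comparison

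*SAP*

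**What the plan says.** Section 2.2 lists, among the outcomes expected to be better with 7 days, "rates of secondary nosocomial infection/colonization with antimicrobial resistant organisms in hospital". Section 5.2 repeats the hypothesis ("We hypothesize that 7 days of treatment will be superior to 14 days of treatment for" this and three other outcomes) and assigns an unadjusted chi-square test.

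The operational definition is in section 3.2.10. The event is "defined as a positive culture yielding a highly resistant microbial organism (HRMO"), counted "from the date of index blood culture until 28 days or hospital discharge whichever is first". The listed organisms include vancomycin-resistant enterococci, extended-spectrum beta-lactamase producers and carbapenem-resistant Enterobacteriaceae. A sensitivity analysis keeps isolates "only from sterile site specimens (such as blood, cerebrospinal fluid, peritoneal fluid, synovial fluid, pleural fluid, and tissue biopsies". Neither rule mentions the index isolate, repeat cultures of it, or resistant organisms found before randomisation.

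**The concern.** Every patient enters the trial with a positive index blood culture (section 3.1). If that isolate is on the 3.2.10 list, the patient satisfies the definition on day 0, whatever is cultured later. Such an event is not secondary. It need not be nosocomial either, because section 5.3 has a community-acquired subgroup. Duration of treatment cannot have caused it.

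Three things are at stake:

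- The reported rate would mix resistance present at entry with resistance acquired afterwards, so it would overstate secondary acquisition.
- A real reduction with 7 days would look smaller on the relative scale and would be easier to miss.
- The sterile-site analysis would be hit harder than the main one. It removes many acquired events, such as colonisation at non-sterile sites, but keeps every index isolate, because the index specimen is blood.

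**Working it through.** **Plan figures.** The SAP states no rate, effect size or power for this outcome, so there is no figure to reproduce. It supplies only the trial size: section 4 gives 1,686 per arm, and 2 × 1,686 × 1.024 × 1.05 = 3,625.6, which matches the stated total of 3,626. Half of that is 1,813 per arm, taken below as 1,800.

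**Assumptions (not in the SAP).** New resistant-organism acquisition is 10% with 14 days and 7.5% with 7 days, a true RR of 0.75. The test is two-sided at 0.05. The share *q* of patients with a resistant index isolate is varied and is equal in the two arms by randomisation.

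**Formula.** With acquisition risk *a*, the observed risk is

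P = q + (1 − q)a.

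The risk difference is then (1 − q)(a14 − a7): it shrinks slightly while both risks rise, so the RR moves toward 1. If a14 = a7, the two observed risks are equal for any *q*, so type I error is not affected.

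**Worked example, q = 5%.** 14 days: 0.05 + 0.95 × 0.10 = 0.145. 7 days: 0.05 + 0.95 × 0.075 = 0.12125. Difference 0.02375; RR 0.84. The average risk is 0.1331, so the standard error under the null is √(2 × 0.1331 × 0.8669 / 1,800) = 0.01132. Under the alternative it is also 0.01132. Power = Φ((0.02375 − 1.96 × 0.01132) / 0.01132) = 55.5%.

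| q | 14 days | 7 days | Difference | RR | Power |
|---|---|---|---|---|---|
| 0% | 10.0% | 7.5% | 2.50 points | 0.75 | 76% |
| 1% | 10.9% | 8.4% | 2.48 | 0.77 | 71% |
| 2% | 11.8% | 9.4% | 2.45 | 0.79 | 67% |
| 5% | 14.5% | 12.1% | 2.38 | 0.84 | 55.5% |
| 10% | 19.0% | 16.8% | 2.25 | 0.88 | 42% |
| 15% | 23.5% | 21.4% | 2.13 | 0.91 | 33% |

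**Sterile-site analysis.** Assume 2.0% versus 1.4% newly acquired (RR 0.70).

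- q = 5%: 0.05 + 0.95 × 0.020 = 0.0690 and 0.05 + 0.95 × 0.014 = 0.0633. RR 0.92. Index isolates make up 0.05 / 0.069 = 72% of the 14-day arm's events.
- q = 10%: 0.118 and 0.1126. RR 0.95. Index isolates make up 0.10 / 0.118 = 85%.

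**After the fix.** Take the pessimistic case in which patients with a resistant index isolate never yield a different resistant organism but stay in the denominator. The risks become (1 − q)a and the RR stays at 0.75. At q = 5% the risks are 9.5% and 7.125%, with power 73%. At q = 10% they are 9.0% and 6.75%, with power 71%.

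**The case against.** **The label may already exclude the index isolate.** Sections 2.2 and 5.2 call the outcome secondary, and an index isolate is not secondary to itself. On that view 3.2.10 merely supplies an organism list and a time anchor, the anchor being the one used for the organ-support free-days. This has some force: an analyst might apply the exclusion unprompted, so a reader should not infer that index isolates will certainly be counted. But 3.2.10 is the rule that will be programmed, and its literal reading includes them. Where the SAP wants the original organism or a later time origin to matter, it says so: relapse in 3.2.3 names the original organism and starts after therapy is completed.

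**The size is assumed.** This stands. No input rate comes from the SAP. At a 1% or 2% share the loss is modest (power 71% or 67% against 76%), and the absolute difference barely moves even at 10% (2.50 to 2.25 points).

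**The error is conservative and confined to a secondary outcome.** This also stands. A reader might infer a bias toward 7 days or a higher false-positive rate. Neither follows, because randomisation balances the extra events in expectation and the chi-square test stays valid.

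**Two extensions are tempting but unsupported.** The *C. difficile* window in 3.2.9 also runs from bacteremia diagnosis, but it needs a positive *C. difficile* test with diarrhea. The index blood culture cannot be such an event, so the mechanism is absent. A reader might also want the count to begin at day 7, because section 5.1 says of early deaths that "these patients die prior to divergence in treatment assignment". Section 5.1 uses that reasoning only for an additional modified intention-to-treat analysis. A day-7 start would change the estimand, and it raises the question of how to treat patients who die or leave hospital before then.

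**Conclusion.** The point holds for section 3.2.10 and its sterile-site analysis only. The definition as written admits resistant index isolates and their repeat cultures, contrary to the outcome named in sections 2.2 and 5.2. The consequence is attenuation and lost power on one of four superiority secondary outcomes, together with an overstated event rate. The primary mortality analysis is untouched.

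The direction holds for any resistant share above zero, provided 7 days truly lowers acquisition. The amount rests on assumed acquisition rates and an unknown share: in the illustration, power falls from 76% to between 71% (1% share) and 42% (10% share). The relative distortion is larger for sterile sites. The point is worth correcting before analysis, but it is not a threat to the trial's main conclusion.

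**What to change.** Add one rule to section 3.2.10: count only a highly resistant organism from a specimen collected after randomisation, and only if that organism was not already recovered in the index blood culture or in another culture before randomisation. Keep all randomised patients in the denominator, so that a patient with a resistant index isolate can still have an event through a different resistant organism. State that the sterile-site analysis follows the same rule. Leave the *C. difficile* window as it is, and do not move the main analysis to a day-7 start.

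The cost is a short text change, fewer counted events in both arms, and matching of organisms across cultures as well as a date filter. This assumes that specimen dates and organism identities were recorded, including for pre-randomisation cultures. The SAP does not say so, and it should be confirmed.
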